6.2.6 Duration of Composite Complete Remission

Duration of composite complete remission (in number of days) is calculated from the first time a composite complete remission is observed to time of relapse defined as above table.

The duration of composite complete remission will be calculated to the last available time point in the case that relapse was not observed.

Duration of composite complete remission will be summarized for subjects who achieved complete remission during the study.

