## 7.2.3 Efficacy Evaluation

### 7.2.3.1 Assessment Based on Response Criteria

The investigator or subinvestigator will evaluate response in each course in accordance with the response criteria in [Table 7.2-1](#), which is based on the response criteria for AML treatment established by an international working group, and will document evaluation results in the medical records and CRF. The evaluation results to be documented in the medical records and CRF will be “not evaluable (NE)” when no bone marrow examination has been performed, “progressive disease” when disease clearly progressed without CR, CRi, or CRp achieved after the start of IMP administration, or “no response” when no remission or relapse has been confirmed in the course.

The best overall response for each subject and the date of the first response (CR, CRi, or CRp) will be documented in the medical records and CRF at the time of trial completion or withdrawal from the trial. Also recorded will be the date of the first relapse, if relapse occurred thereafter, and the date of the last evaluation, if no relapse occurred.

Table 7.2-1 Response Criteria		
	Bone Marrow	Peripheral Blood
CR	
 
Blast cells < 5%
 
	
 
Neutrophil count > 1,000/<math>\mu</math>L
 
Platelet count <math>\geq</math> 100,000/<math>\mu</math>L
 
No blast cell
 
Transfusion independence
 

CRp	
 
Blast cells < 5%
 
	
 
Neutrophil count > 1,000/<math>\mu</math>L
 
Platelet count < 100,000/<math>\mu</math>L
 
No blast cell
 
RBC transfusion independence
 

Morphologic CRi	
 
Blast cells < 5 %
 
	
 
Neutrophil count < 1,000/<math>\mu</math>L
 
No blast cell
 

PR	
 
Rate of decrease in blast cells in the bone marrow <math>\geq</math> 50% and ratio of blast cells of 5% to 25%
 
	
 
Neutrophil count > 1,000/<math>\mu</math>L
 
Platelet count <math>\geq</math> 100,000/<math>\mu</math>L
 
No blast cell
 

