### **11.2 Handling of Data**

- 1) Acceptable time windows of timepoints for examinations  
The acceptable time windows of timepoints for examinations to be used in tabulation are detailed in the statistical analysis plan.
- 2) Handling of missing data  
How to handle missing data is described in the statistical analysis plan.
- 3) Handling of events and censoring  
In the analysis of overall survival, all deaths (regardless of cause) will be defined as events, and time to death from the start date of IMP administration will be analyzed. If subjects are alive at the end of the primary evaluation part, they will be censored (the day of survival confirmation will be the day of censoring).

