### 11.3.2 Efficacy Analysis

- 1) Definitions

- a) Evaluation of the complete remission rate (CR), composite complete remission rate (CR + CRi + CRp), and overall remission rate (CR + CRi + CRp + PR) based on the response criteria for AML treatment established by an international working group (with partial modifications)
- b) Composite complete remission duration
- c) Overall survival

- 2) Analysis set  
Efficacy analysis set
- 3) Analysis methods
  - a) Remission  
Data will be summarized by cohort as follows:
    - Assessment in each course (CR, CRp, CRi, PR, no response, progressive disease, or NE)
    - Distribution of the best overall response: complete remission rate (CR), composite complete remission rate (CR + CRi + CRp), and overall remission rate (CR + CRi + CRp + PR)
  - b) Composite complete remission duration  
Descriptive statistics of time from the first composite complete remission to relapse will be calculated for subjects who have achieved composite complete remission.
  - c) Overall survival  
A Kaplan-Meier plot will be generated for each cohort that includes at least 6 treated subjects.

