6.2.7 Overall Survival

Overall survival is defined as the number of days from the day the subject received the first dose of IMP to the date of death (regardless of cause).

Survival time will be censored on the last date of survival confirmation if a subject is alive or lost to follow-up.

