10.2 Duration of Composite Complete Remission

The following analysis will be conducted by cohort and overall (Cohorts 1, 2, and 4) for the subjects with composite complete remission.

- Summary of duration of composite complete remission using descriptive statistics.

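### Duration of composite complete remission is summarised without censoring, so remissions still ongoing pull the reported mean down

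*SAP*

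**What the plan says.** SAP 6.2.6 runs the duration from the first composite complete remission to relapse. For responders without relapse it adds: "The duration of composite complete remission will be calculated to the last available time point in the case that relapse was not observed". SAP 10.2 plans only this: "Summary of duration of composite complete remission using descriptive statistics", by cohort and for Cohorts 1, 2 and 4 pooled. Protocol 11.3.2 has the same type of summary and no rule for responders who do not relapse: "Descriptive statistics of time from the first composite complete remission to relapse will be calculated for subjects who have achieved composite complete remission".

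Overall survival is treated differently. Protocol 11.2 states "If subjects are alive at the end of the primary evaluation part, they will be censored", SAP 6.2.7 states "Survival time will be censored on the last date of survival confirmation if a subject is alive or lost to follow-up", and SAP 10.3 uses Kaplan-Meier. These are the only censoring rules in the two documents. SAP Section 13 lists no change for remission duration.

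The population is also stated in two ways. SAP 6.2.6 ends with "Duration of composite complete remission will be summarized for subjects who achieved complete remission during the study", and SAP 6.2.3 defines complete remission as CR only. SAP 10.2 says "The following analysis will be conducted by cohort and overall (Cohorts 1, 2, and 4) for the subjects with composite complete remission", which by SAP 6.2.4 includes CRp and CRi.

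**The concern.** For a responder still in remission, the time to the last available point is a lower bound on the duration. The SAP does not call that point a censoring date, and plain descriptive statistics could not use it as one. The incomplete time is averaged with completed ones.

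The design makes such responders foreseeable. Relapse leads to withdrawal (Protocol 9.2, item 1). Subjects still on treatment at the cutoff may enter the extended part (Protocol 3.1). Efficacy endpoints belong to the primary part only (Protocol 3.3.2), and the extended courses list only symptoms and hematology (Protocol 7.1.4.1.13 and 7.1.4.2.17). A composite responder who enters the extended part is therefore relapse-free by rule, and the recorded duration is incomplete. The subjects who do best are the ones cut short.

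Composite remission duration is a named efficacy endpoint, and with very few responders one cut value can set the reported figure. Separately, the last sentence of SAP 6.2.6, read literally, drops CRp and CRi responders.

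**Working it through.** The plan states no figure for this endpoint, so there is none to reproduce. The numbers below show direction and plausible size.

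**Inputs**
- Primary-part windows (Protocol 15): 01 Oct 2014 to 31 May 2016 = 608 days (Cohorts 1, 2, 4); 01 Sep 2016 to 30 Nov 2017 = 455 days (Cohort 3).
- Remission duration in the earlier study (Protocol 1.2.2.1.1.1): median 114 days, range 42 to 558. It is preliminary, from five AML responders, and the text does not say whether ongoing remissions were censored.
- Composite remission rates (Protocol 1.2.2.1.1.2): 16% in relapsed or refractory AML, 53% in elderly treatment-naïve AML.
- Cohort sizes (Protocol 3.4): 6 in Cohort 3, 3 to 6 in the others. The pooled row has 12 to 18 subjects if escalation reaches Cohort 4.

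**Direction.** If responder *i* has true duration T and is relapse-free at C, the plan records C < T. The mean of *n* responders falls by the sum of (T − C) over the ongoing ones, divided by *n*. The median moves only if a cut reaches a value that determines the middle of the ordered durations. With one or two responders, median and mean coincide.

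**Three-responder illustration.** Assume true durations of 42, 114 and 558 days: mean 714/3 = 238, median 114. Take the earliest possible first dose and a Day 29 remission:

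| Case | Longest observable (days) | Plain mean |
|---|---|---|
| Cohort 1 | 608 − 28 = 580 | 238 |
| Cohort 2 | 608 − 28 − 28 = 552 | 708/3 = 236 |
| Cohort 4 | 608 − 56 − 28 = 524 | 680/3 = 226.7 |
| Cohort 3 | 455 − 28 = 427 | 583/3 = 194.3 |
| Cohort 3, mid-window first dose | 455 − 228 − 28 = 199 | 355/3 = 118.3 |

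The median is 114 throughout.

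**Exponential model (assumption).** Rate L = ln 2/114; true mean 1/L = 164.5 days. The expected plain mean is 164.5 × (share relapsed): with 10%, 25% or 50% not relapsed it is 148.0, 123.4 or 82.2.

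Now spread first doses evenly over the first 50% or 75% of the window, put remission at 28 or 84 days, and let only the cutoff censor. Follow-up after remission is then uniform on (lo, hi), and the share not relapsed is [exp(−L·lo) − exp(−L·hi)] / [L(hi − lo)]:

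| Cohorts | Entry / onset | lo–hi (days) | Not relapsed | Plain mean | Large-sample plain median |
|---|---|---|---|---|---|
| 1, 2, 4 | 50% / 28 d | 276–580 | 8.5% | 150.5 | 114 |
| 1, 2, 4 | 50% / 84 d | 220–524 | 12.0% | 144.8 | 114 |
| 1, 2, 4 | 75% / 28 d | 124–580 | 15.9% | 138.3 | 114 |
| 1, 2, 4 | 75% / 84 d | 68–524 | 22.4% | 127.7 | 101 |
| 3 | 50% / 28 d | 199.5–427 | 16.1% | 138.0 | 114 |
| 3 | 50% / 84 d | 143.5–371 | 22.6% | 127.2 | 114 |
| 3 | 75% / 28 d | 85.8–427 | 25.0% | 123.3 | 105 |
| 3 | 75% / 84 d | 29.8–371 | 35.2% | 106.6 | 85 |

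Medians are simulated.

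**Chance that at least one remission is ongoing**, with p the share not relapsed:
- *Given n responders*, 1 − (1 − p)^n. Cohorts 1, 2, 4: 8.5–22.4% with one, 23–53% with three. Cohort 3: 16.1–35.2% with one.
- *Before responders are known*, 1 − (1 − rp)^N with response rate r. Cohort 3 (N = 6, r = 0.16): 14.5–29.4%. One other cohort of 6: 8–20% at r = 0.16, 24–53% at r = 0.53. Pooled row (N = 12 to 18): 15–48% at 0.16, 42–90% at 0.53.

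Expected responders are 6 × 0.16 = 0.96 in Cohort 3, and 0.96 to 6 × 0.53 = 3.18 in any other cohort of 6.

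**What censoring does.** Assume true durations 42, 90, 114, 200 and 558 (mean 200.8, median 114), with the last two seen relapse-free only to 60 and 100 days. The plain mean is 406/5 = 81.2 and the plain median 90. The Kaplan-Meier curve drops to 0.80 at 42 days, 0.53 at 90 and 0 at 114, so its median is 114.

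**The case against.** - **Direction depends on the date used.** The SAP does not say which date it means. A later survival contact (Protocol 7.2.3.2) could carry a duration past an unseen relapse. After Course 1, marrow is taken only when blood counts suggest remission or progression is clear, so relapse may also be dated late. This stands, and it is a reason to name the date. It does not alter the result for a remission truly ongoing at that date.
- **A mean is inferred.** Neither document lists the statistics for this endpoint, and the median often does not move. That is true, but a mean is a usual part of such a summary, and nothing would mark the ongoing values.
- **The 118-day case is constructed.** It gives the 558-day extreme one-third weight and puts all three responders at mid-window. With the five assumed values above, a 199-day cap gives 128.8 against 200.8 (−36%) and a 427-day cap gives −13%. This stands; it is an illustration, not an estimate.
- **The model is rough.** The 16% and 53% rates come from 60 and 90 mg/m² but are applied to Cohort 1 and the pooled row as well. The 53% end needs every subject to be elderly and treatment-naïve. Starting Cohort 4 on day 56 gives 9.6–24.8% not relapsed in place of 8.5–22.4%. In Cohort 3 there would be no ongoing remission about 71–86% of the time.
- **The CR wording is a slip.** The section title, SAP 10.2 and the protocol all say composite. Agreed, but it still needs correcting.
- **Interim results.** SAP Section 4 has an interim analysis of Cohorts 1, 2 and 4 on data locked 25 Aug 2017. A changed method could give a different final figure for those cohorts. This is a real, small cost. The pre-analysis data review in the same section could settle the date field and deaths in remission, but it is no substitute for a written rule.

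**Conclusion.** The concern holds. Followed as written, the plan understates mean composite remission duration whenever a responder is relapse-free at the last response evaluation. That direction is certain for such a responder; the size is not fixed by the documents. Under the stated exponential and entry assumptions, the expected mean falls from 164.5 days by 8.5 to 22.4% in Cohorts 1, 2 and 4 and by 16.1 to 35.2% in Cohort 3. The large-sample median falls by 0 to 11% and 0 to 26%. Withdrawal while in remission would add to this. A single cohort may well have no ongoing remission; the pooled row is more likely to have one. The endpoint is secondary and descriptive, with no tests or intervals (SAP 6.5), and neither DLT assessment nor cohort transition depends on it. It should be corrected because the reported duration can mislead and the remedy is cheap.

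**What to change.** Change SAP 6.2.6 and 10.2 as follows:
- Make relapse the event. Censor responders without relapse at the date that Protocol 7.2.3.1 already records: "the date of the last evaluation, if no relapse occurred". Use this in place of the undefined last time point.
- Report the number relapsed and the number ongoing.
- List individual durations with a plus sign for ongoing remissions. Name this listing in the SAP, because SAP Section 1 leaves listings out unless stated.
- Give the Kaplan-Meier median where it can be estimated, in place of the plain mean and median.
- Count deaths in remission separately and state how they are handled.
- Replace complete remission with composite complete remission in the last sentence of SAP 6.2.6.
- Record the change from Protocol 11.3.2 in SAP Section 13, and note there any difference from the interim results for Cohorts 1, 2 and 4.

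The cost is SAP wording, one table and a short listing. No new data are needed: relapse, last-evaluation and death dates are already collected (Protocol 7.2.3.1 and 7.2.3.2), and Kaplan-Meier is already planned for survival at any cohort size (SAP Section 13). With very few responders the Kaplan-Meier median may be unstable or not reached, so the listing and the ongoing count will carry most of the information.

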6.2.7 Overall Survival

Overall survival is defined as the number of days from the day the subject received the first dose of IMP to the date of death (regardless of cause).

Survival time will be censored on the last date of survival confirmation if a subject is alive or lost to follow-up.

6.3 Handling of Time Points

Data recorded at the time points specified in the case report form will be summarized for the respective time points. If data at the time of withdrawal or unspecified time points are within the acceptable time window specified in the protocol, they will be used as the data at that time point. If there are 2 or more data in a specific time window, the closest data to the scheduled visit date will be used for the analysis. If there are 2 data with same interval from the scheduled visit date, one before the scheduled visit date and the other after the scheduled visit date, the data from after the scheduled visit date will be used for the analysis. If 2 or more data are collected on the same date, the mean value of these data will be used for the analysis.

Baseline is defined as last available data before the first dose of IMP.

Time point of Cohort 3 vital sign data will be handled same as the time point of Cohorts 1, 2 and 4.

6.4 Handling of Missing Values and Outliers

No imputation of missing values or exclusion of outliers will be performed.

6.5 Significance Level and Confidence Coefficient

No significance level or confidence coefficient will be set, since statistical tests and interval estimations will not be performed.

6.5.1 Multiple Comparisons and Multiplicity

No multiple comparisons and multiplicity will be considered, since statistical tests will not be performed.

7 Disposition of Subjects

Subjects who gave informed consent will be used in the statistical analyses. Data will be summarized by cohort and overall (Cohorts 1, 2, and 4).

7.1 Disposition of Subjects

Subject disposition will be summarized. The frequency distribution (number of subjects and incidence rate [the same applies hereafter]) of subjects who gave informed consent, screen failures, subjects who were administered the IMP, subjects who completed course 1, and subjects who discontinued the study will be determined. In addition, the frequency distribution of study discontinuation will also be determined by primary reason for discontinuation.

Frequency distribution will be summarized for course 1 and on or after course 2. Only the subjects who continue IMP administration on or after course 2 will be included in the frequency distribution for on or after course 2.

7.2 Statistical Analysis Sets

The frequency distribution of subjects included or excluded in each analysis set will be determined for subjects who were administered the IMP.

8 Description of Analysis Datasets

The safety analysis set will be used in the statistical analyses. The following analyses will be performed by cohort and overall (Cohorts 1, 2, and 4).

8.1 Demographics and Baseline Characteristics

Demographic and other baseline characteristics are as follows;

- 1) Age (< 65 years, ≥ 65 and < 75 years, ≥ 75 years, calculated relative to date of informed consent)
- 2) Sex (Male, Female)
- 3) Height (cm)
- 4) Weight (kg)
- 5) Body surface area (m^2)
- 6) Eastern Cooperative Oncology Group (ECOG) Performance Status (PS) (0, 1 or 2)
- 7) Diagnosis of AML
- 8) Time since initial diagnosis (calculated relative to date of first dose of IMP)
- 9) Hematopoietic stem cell transplantation history (Yes, No) and type of transplantation
- 10) De novo or secondary AML (De novo AML, secondary AML)
- 11) Prior radiotherapy history (Yes, No)
- 12) Chemotherapy history including induction therapy history and consolidation therapy history
- 13) Poor type category of Karyotype at screening (Better risk, Intermediate risk, Poor risk, Unknown)
- 14) Cytogenetic abnormalities (Yes, No, Unknown) and detail of abnormality
- 15) Extra medullary lesions found after diagnosis of AML (Yes, No)
- 16) Maximum proportion of blast cells (leukemic cells) in the bone marrow after diagnosis of AML
- 17) Baseline leukocytes ($\geq 20.0 \times 10^9/L$, ≥ 2.0 and < $20.0 \times 10^9/L$, ≥ 1.0 and < $2.0 \times 10^9/L$, < $1.0 \times 10^9/L$)
- 18) Baseline neutrophil ($\geq 1.0 \times 10^9/L$, ≥ 0.5 and < $1.0 \times 10^9/L$, < $0.5 \times 10^9/L$)
- 19) Baseline platelets ($\geq 50.0 \times 10^9/L$, ≥ 25.0 to < $50.0 \times 10^9/L$, < $25.0 \times 10^9/L$)

1) will be summarized with descriptive statistics in addition to categorical summary. 3), 4), 5), 8) and 16) will be summarized with descriptive statistics. Others will be summarized categorically.

In detail, poor-risk cytogenetics is defined based on the National Comprehensive Cancer Network (NCCN) Guidelines[®] (2014)² as follows:

Risk Status Based on Cytogenetics¹

Risk Status	Cytogenetics
Better-risk	inv(16) ^{2,3} or t(16;16) ² t(8;21) ² t(15;17)
Intermediate-risk	Normal cytogenetics +8 alone t(9;11) Other non-defined
Poor-risk	Complex (≥ 3 clonal chromosomal abnormalities) Monosomal karyotype -5, 5q-, -7, 7q- 11q23 - non t(9;11) inv(3), t(3;3) t(6;9) t(9;22) ⁴

¹ The molecular abnormalities included in this table reflect those for which validated assays are available in standardized commercial laboratories. Given the rapidly evolving field, risk stratification should be modified based on continuous evaluation of research data. Other novel genetic mutations have been identified that may have prognostic significance.

² Other cytogenetic abnormalities in addition to these findings do not alter better risk status.

³ Paschka P, Du J, Schlenk RF, et al. Secondary genetic lesions in acute myeloid leukemia with inv(16) or t(16;16): a study of the German-Austrian AML study group (AMLSG). Blood 2013;121:170-177.

⁴ For Philadelphia+ AML t(9;22), manage as myeloid blast crisis in chronic myeloid leukemia, with addition of tyrosine kinase inhibitors.

Source: NCCN Guidelines: Acute Myeloid Leukemia. Version 2.2014. NCCN.org.

8.2 Status of Trial Conduct

8.2.1 Investigational Medicinal Product Compliance

Not applicable.

8.2.2 Use of Medication Other Than Investigational Medicinal Product

Medications will be coded using World Health Organization Drug Dictionary (WHO-DD) version 01MAR2014.

The frequency distribution for the use of medications other than the IMP will be determined by therapeutic subgroup [Anatomical Therapeutic Chemical (ATC) level 2] and preferred term.

- Medications used before the start of IMP administration
- Medications used during the trial period (from the start of IMP administration to the end-of-trial assessment)

8.2.3 Number of Blood Transfusion

Frequency distribution of the number of subjects who received transfusion by the type of blood transfusion for each course including baseline will be summarized by cohort and overall (Cohorts 1, 2, and 4).

The number of blood transfusions (units/ month) over the treatment period will be calculated by the type of blood transfusion and subjects and will be summarized by cohort and overall (Cohorts 1, 2, and 4).

9 Safety Analysis

The safety analysis set or DLT evaluation analysis set will be used in safety analyses. The following analyses will be conducted by cohort and overall (Cohorts 1, 2, and 4) for subjects receiving IMP.

9.1 Extent of Exposure

Safety analysis set will be used for the analysis.

The following items will be tabulated.

- Frequency distribution of the number of IMP administrations on course 1.
- Frequency distribution of the number of IMP dosed subjects for each course
- Number of IMP administration courses for each subject will be summarized with descriptive statistics for the overall treatment period.

9.2 Primary Endpoints

DLT is the primary endpoint of this trial.

DLT evaluation analysis set will be used for the analysis.

- DLTs [preferred term (PT)] which observed on course 1 will be tabulated (number of subjects and incidence rate) by DLT criteria and Medical Dictionary for Regulatory Activities (MedDRA) system organ class (SOC) and PT.

9.3 Secondary Endpoints

The safety analysis set will be used for the analysis.

9.3.1 Adverse Events

AEs will be coded using MedDRA version 20.0.

- The number of subjects and incidence will be summarized for all treatment-emergent AEs (TEAEs).
- The number of subjects and incidence will be summarized for all TEAEs by MedDRA SOC and PT.
- The number of subjects and incidence will be summarized for all TEAEs by MedDRA SOC, PT, and CTCAE grade. If a subject experiences the same TEAE 2 or more times, the most severe grade occurrence will be used for the analysis.
- The number of subjects and incidence will be summarized for all TEAEs by the timing of AE occurrence (in course 1, in or after course 2, and overall), MedDRA SOC and PT. AEs which had occurred in Course 1 and continued beyond course 2 will be included in “in or after course 2” category.

- TEAEs that DLTs and correspond to DLTs (preferred term) which were observed in course 1, in or after course 2, and overall will be tabulated (number of subjects and incidence rate). AEs which had occurred in Course 1 and continued beyond course 2 will be included in “in or after course 2” category.

Adverse drug reactions (TEAEs for which a causal relationship with the IMP are suspected adverse reaction) will be summarized in the same manner as above.

9.3.2 Death, Other Serious Adverse Events, CTCAE Grade 3 or above Adverse Events, and Other Significant Adverse Events

The following TEAEs will be summarized in the same manner as in first bullet of [Section 9.3.1 Adverse Events](#). Also the following TEAEs, excluding TEAEs of grade ≥ 3 , will be summarized in the same manner as in second bullet of [Section 9.3.1 Adverse Events](#).

- Serious TEAEs
- TEAEs leading to death
- TEAEs leading to discontinuation in course 1, in or after course 2, and overall
- TEAEs of grade ≥ 3
- TEAEs leading to postponement of the start of the next course
- TEAEs leading to skipping of IMP administration

Adverse drug reactions (TEAEs for which a causal relationship with the IMP are suspected adverse reaction) will be summarized in the same manner as above.

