**11.3.1.2 Secondary Endpoints**

1) Definitions

- a) AEs
- b) Clinical laboratory values
- c) Vital signs (blood pressure, pulse rate, and body temperature) and body weight
- d) ECOG PS
- e) Twelve-lead ECG
- f) Chest X-ray

2) Analysis set

Safety analysis set

3) Analysis method

a) Adverse events

The following tabulations will be performed for each cohort:

- All AEs occurring after the start of IMP administration (treatment-emergent adverse events) (all events, SOCs, and PTs) will be summarized using the Medical Dictionary for Regulatory Activities (MedDRA).
- Adverse events will be summarized (number and percentage of subjects with AEs) by CTCAE grade.  
However, if an event occurs more than once in the same subject, the most severe episode will be included in the tabulation.
- Adverse events in treated subjects in each course will be summarized (number and percentage of subjects with AEs) by timing of occurrence.
- Deaths, other SAEs, and AEs leading to discontinuation will be summarized.
- Adverse drug reactions (AEs assessed as related to the IMP) will be summarized in the same manner as AEs.
- Dose-limiting toxicities (including events occurring after the start of Course 2) will be summarized (number and percentage of subjects with DLTs).

b) Clinical laboratory values

Hematological and blood biochemistry data at each timepoint will be summarized by cohort as follows:

- Descriptive statistics of measurements
- Descriptive statistics of change from baseline

- A shift table of the value at the last evaluation and the worst value after the treatment relative to the baseline value by CTCAE grade

Urinalysis data at each timepoint will be summarized by cohort as follows:

- A shift table of the value at the last evaluation and the worst value after the treatment relative to the baseline value by CTCAE grade

- c) Vital signs (blood pressure, pulse rate, and body temperature) and body weight

Vital signs (blood pressure, pulse rate, and body temperature) and body weight at each timepoint will be summarized by cohort as follows:

- Descriptive statistics of measurements
- Descriptive statistics of change from baseline

- d) Eastern Cooperative Oncology Group performance status

Eastern Cooperative Oncology Group PS at each timepoint will be summarized by cohort (the number and percentage of subjects for each score).

- e) Twelve-lead electrocardiogram

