5.1.1 Safety Analysis Set

The safety analysis set will include subjects who have received at least one dose of the IMP.

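### Adverse-event, DLT and discontinuation percentages for Course 2 onward are not restricted to subjects dosed in Course 2

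*SAP*

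**What the plan says.** SAP 9.3 names one population for all secondary safety tables: "The safety analysis set will be used for the analysis". SAP 5.1.1 defines it: "The safety analysis set will include subjects who have received at least one dose of the IMP". No dose in Course 2 is needed to belong.

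Within that frame, SAP 9.3.1 summarises treatment-emergent events "by the timing of AE occurrence (in course 1, in or after course 2, and overall"). It also summarises DLTs and events corresponding to DLTs "which were observed in course 1, in or after course 2, and overall will be tabulated (number of subjects and incidence rate"). SAP 9.3.2 uses the same three periods for events leading to discontinuation, and adverse drug reactions follow the same pattern. None of these entries states a denominator for the later period. After each of the two timing entries in 9.3.1 comes a carry-over rule: "AEs which had occurred in Course 1 and continued beyond course 2 will be included in" the later-period category.

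Two other places treat the later period differently. Protocol 11.3.1.2, under the same safety analysis set, says: "Adverse events in treated subjects in each course will be summarized (number and percentage of subjects with AEs) by timing of occurrence". SAP 7.1, on disposition from Course 2 onward, says: "Only the subjects who continue IMP administration on or after course 2 will be included". SAP Section 13 lists three changes from the protocol (urinalysis categories, the interim analysis and the Kaplan-Meier plots). The by-course adverse-event table is not among them.

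**The concern.** Every subject in the safety analysis set has been dosed in Course 1, so that set is a sound denominator for Course 1. It is not one for the later period. Course 2 is optional, and Protocol 3.1 opens it only to subjects who complete the DLT evaluation period without apparent progression. Some treated subjects may therefore never be exposed in the period that the column describes. A subject who stops after Course 1 cannot contribute a new Course 2 event but, on the literal reading, still enlarges the denominator.

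A programmer who sees the restriction in 7.1 and not in 9.3.1 or 9.3.2 could reasonably take the difference as intended. The percentages would then depend on how many subjects continued as well as on how often events occurred among those who did, and cohorts with different continuation would not be comparable. Evaluating safety through adverse events is a stated secondary objective, so the column should have a clear meaning.

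**Working it through.** The documents give no figure for later-period incidence, so there is nothing to reproduce. The check compares the two candidate denominators.

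**Inputs**
- N, subjects in the safety analysis set: 6 in Cohort 3 and 3 to 6 in each of Cohorts 1, 2 and 4 (Protocol 3.4). The SAP's pooled column covers Cohorts 1, 2 and 4, so at most 3 × 6 = 18.
- m, subjects dosed in Course 2: not known for this trial. SAP 9.1 will tabulate the number dosed in each course, so m will be available.
- Illustrative m/N: 67% and 78%, the shares given 2 cycles in the dose escalation and dose expansion segments of Study SGI-110-01 (Protocol 1.2.2.1.1.1 and 1.2.2.1.1.2). Using them here is an assumption.
- x, subjects with an event in the later period, all assumed to have been dosed in Course 2.

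**Formula**

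On the safety set the percentage is x/N. Among those dosed in Course 2 it is x/m. Since x/N = (x/m) × (m/N), the literal reading scales the at-risk percentage by m/N. For x above zero, the result is lower whenever m is below N.

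**Numbers, carry-over ignored**

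| N | m | x | x/N | x/m |
|---|---|---|---|---|
| 6 | 4 (0.67 × 6 = 4.02) | 1 | 16.7% | 25.0% |
| 6 | 4 | 2 | 33.3% | 50.0% |
| 6 | 5 (0.78 × 6 = 4.68) | 1 | 16.7% | 20.0% |
| 6 | 5 | 2 | 33.3% | 40.0% |
| 18 | 12 (0.67 × 18 = 12.06) | 2 | 11.1% | 16.7% |
| 18 | 14 (0.78 × 18 = 14.04) | 2 | 11.1% | 14.3% |

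In general terms, an at-risk incidence of 40% would print as 0.67 × 40 = 26.8% to 0.78 × 40 = 31.2%.

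**Effect of the carry-over rule**

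Take N = 6, m = 4 and one subject with a new-onset event, so that new-onset incidence among those at risk is 1/4 = 25.0%. Let k other continuing subjects have a Course 1 event that persists.

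| k | (1 + k)/N | (1 + k)/m |
|---|---|---|
| 0 | 16.7% | 25.0% |
| 1 | 33.3% | 50.0% |
| 2 | 50.0% | 75.0% |

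With k = 1 the literal percentage (33.3%) already exceeds the new-onset incidence. With the numerator held fixed, the safety-set figure is still the lower of the two. Denominator and carry-over are therefore separate problems, and correcting only the first would print 75.0% at k = 2 against a new-onset incidence of 25.0%.

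**Where the protocol fills the gap**

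For the by-timing adverse-event table, Protocol 11.3.1.2 points to the subjects treated in each course. For later-course DLTs and for events leading to discontinuation it asks only for a summary, so neither document gives a course-specific denominator there.

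**The case against.** The best defence is that the SAP nowhere says that subjects without Course 2 count in the later column. It names an analysis set, and Protocol 11.3.1.2 names the same set while summarising events in the subjects treated in each course. Naming the safety set is thus compatible with a course-specific denominator, and Section 13 declares no departure. This stands in part. A reader might infer that the SAP expressly prescribes the whole-set denominator, and the documents do not support that. But the SAP drops the protocol's qualifier and pools all later courses into one column, and the protocol offers no rule for DLTs or discontinuations. The same edit is needed whichever denominator was meant.

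A second inference is that later-course toxicity must look lower than Course 1 toxicity. The documents do not support this either, because the carry-over rule raises the later numerator and can offset or reverse the effect.

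Third, the 67% and 78% come from another study that enrolled both AML and MDS; the 67% also pools three dosing schedules. They cannot be read as this trial's continuation rate.

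Finally, everything here is descriptive, cohorts are small, and SAP 9.1 reports the numbers dosed per course, so a careful reader could recompute. That limits the harm but leaves the printed percentages without a clear meaning.

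**Conclusion.** The point holds as a gap in specification that, followed literally, gives the wrong denominator. SAP 9.3, 9.3.1 and 9.3.2 apply the safety analysis set to the later-period columns without limiting them to subjects dosed in Course 2. For the adverse-event table this is an undeclared departure from Protocol 11.3.1.2, and throughout it is inconsistent with SAP 7.1.

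The size is the factor m/N, which the documents do not give for this trial. Under the assumed 67% to 78%, a later-period percentage would be about two-thirds to four-fifths of the at-risk value for the same numerator. The net direction relative to Course 1 cannot be stated. The primary endpoint is untouched: SAP 9.2 analyses Course 1 DLTs in the DLT analysis set, and the escalation and MTD rules rest on DLTs in the DLT evaluation period.

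**What to change.** 1. In SAP 9.3.1 and 9.3.2, define the denominator for the later period as subjects with at least one dose in Course 2, for adverse events, adverse drug reactions, DLT-type events and discontinuations. Print that n in the column header.
2. In 9.3.1, show new-onset events separately from those carried over from Course 1, and say exactly when an event counts as carried over.
3. Either restore the protocol's by-course adverse-event table, with the subjects dosed in that course as denominator, or declare its replacement in Section 13.

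Optionally, a listing can show which Course 2 regimen (10-day or 5-day) each Cohort 3 subject received. With 6 subjects planned, a separate table is not needed.

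The cost is a few lines of SAP text and minor reprogramming. No new data are needed, since SAP 9.1 already requires the counts. The drawback is smaller denominators, so each subject moves the percentage more; counts should be printed beside percentages.
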